Graphically displayed over follow-up times (1, 3, 6 and 12 months) using boxplots containing the median, quartiles and outliers. At each follow-up time point (1,3, 6 and 12 months) we will assess whether 80°C and 90°C RFA temperatures differ with respect to the percentage of pain relief using the Wilcoxon rank-sum test. The significance criterion will be 0.05/4=0.0125 at each time, using a Bonferroni correction to control the type I error at 0.05 for the primary hypothesis. In addition to the P-value, the estimated median percentage of pain relief for each group and difference in medians with confidence intervals will be reported. The estimated probability of pain relief at 90°C being better than at 80°C with confidence interval will be reported, since the Wilcoxon rank sum test has a null hypothesis that this probability is 0.50. All the confidence intervals will be estimated based on bootstrapped standard error with 10,000 bootstrap replications (8).

Interim analyses:

Interim analyses will be conducted for efficacy and futility at each 25% of the maximum enrollment (see Sample Size Considerations) using a group sequential design and gamma spending function (using gamma = -4 for efficacy and -2 for futility). P-value boundaries for efficacy (futility in parentheses) will be P \leq 0.0016 (P>0.957), P \leq 0.0048 (P>0.719), P \leq 0.0147 (P>0.239), and P \leq 0.0440 (P>0.0040) at looks 1 through 4, respectively.

• Secondary hypotheses: We will compare randomized groups on the following variables:

VAS pain scores/Pain Disability Index (PDI)/McGill Pain questionnaire scores/Beck Inventory (BI) scores.

While the detailed description below focuses on the VAS pain score outcome for brevity, the analysis approach will be the same for Pain Disability Index (PDI), McGill Pain questionnaire scores, and Beck Inventory (BI) scores.

Graphical analysis will be undertaken to describe the degree of pain reduction observed in patients undergoing each treatment. The association between RFA temperature and pain reduction will be performed using a mixed effects model adjusting for time interval and also for baseline pain score to increase precision. We will assess the group-time interaction and assess treatment effects at each time if interaction P <0.15. The mixed model will account for potential intra-subject correlation of repeated VAS pain measurements within a patient using a spatial

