Sample size estimation is based on the frequency distribution estimated across four categories of pain relief used in our preliminary retrospective study. Thus, for these calculations 38%, 9%, 37%, and 16% of patients undergoing RFA at 80°C are assumed to develop no improvement (=0%), minimal improvement (<25%), moderate improvement (25-75%), and marked improvement (>75%) in symptoms, respectively. We further assumed that the data was uniformly distributed across each category through simulation, and performed power calculations on the simulated data using categories of percent pain relief of 0, 1-10, 11-20, 21-30, \dots , 91 – 100. In order to have 90% power at the 0.0125 significance level at each time point (0.05/4 = 0.0125 at each time point) to detect a clinically significant shift in improvement of absolute 15% between RFA at 90°C and RFA at 80°C, a maximum of N=216 total patients would be required. Below we list the proportion of patients in each percent pain relief category as assumed for the sample size calculations described above. Although a 20% increase is in general what would be considered a clinically important improvement in pain relief, we plan for 15% since there may be a nontrivial fraction of patients who experience no relief in either group. Adjusting for 3 interim analyses and a final analysis would require a maximum of N=237. With the above parameters, there will be a cumulative 8%, 37%, 75%, and 100% chance of crossing a boundary at the 1st through 4th analyses if the alternative hypothesis is true as stated above.

Group	0	1-10	11-20	21-30	31-40	41-50	51-60	61-70	71-80	81-90	91-100
Control	.38	.041	.035	.06	.07	.067	.069	.087	.062	.057	.072
Experimental	0	0	.399	.041	.03	.083	.068	.064	.077	.078	.16

We plan to re-estimate sample size after obtaining at least 1 and 3 month continuous pain relief outcome for the first 60 patients, using the observed shape of the distribution and the variability of the outcome, but still based on an absolute 15 percent upward shift from the 80 degrees group. Type I error will be controlled using the methods in Kieser 2000 (9).

We will provide results to the Data and Safety Committee on efficacy and safety assessments, including conditional power analyses, but the committee will have final say on whether the study would progress to the next interim analysis or be stopped.

References

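### Estimates and intervals for the primary outcome ignore the four-look stopping rule: coverage is moderately low near the planned effect, and estimates are clearly too large after efficacy stops at looks 1 and 2

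*Combined protocol and SAP*

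**What the plan says.** Under Data Analysis, Primary Hypothesis, the two temperatures are compared at 1, 3, 6 and 12 months by the Wilcoxon rank-sum test: "The significance criterion will be 0.05/4=0.0125 at each time". Beside the P-value, "the estimated median percentage of pain relief for each group and difference in medians with confidence intervals will be reported". The plan adds: "The estimated probability of pain relief at 90°C being better than at 80°C with confidence interval will be reported". For the method: "All the confidence intervals will be estimated based on bootstrapped standard error with 10,000 bootstrap replications". No confidence level is given.

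The Interim analyses paragraph follows directly: "Interim analyses will be conducted for efficacy and futility at each 25% of the maximum enrollment", with gamma spending ("using gamma = -4 for efficacy and -2 for futility") and printed efficacy P boundaries of 0.0016, 0.0048, 0.0147 and 0.0440. Sample size considerations states that, under the alternative, "there will be a cumulative 8%, 37%, 75%, and 100% chance of crossing a boundary" at looks 1 to 4.

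The adjustments named are all on the testing side: Bonferroni, the spending boundaries, and type I error control for the sample size re-estimation. No section names a median-unbiased, bias-adjusted, stagewise-ordering or repeated-interval method, or says that the bootstrap follows the stopping rule.

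**The concern.** An ordinary bootstrap resamples the data in hand at the stop. It treats that sample size as fixed, although the sample size was chosen partly by the result. A trial that stops at a high early boundary has, on average, an estimate above the truth, and the standard interval does not allow for this. The reported interval can also disagree with the boundary that stopped the trial.

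The trial is meant to say how much better 90°C is. Sample size considerations calls a 20-point gain generally important and plans for 15. An estimate pushed from about 16 points to well above 20 by stopping at look 1 or 2 would change how the result is read.

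**Working it through.** **Inputs.** The category table, N=216 and N=237, 90% power and the 0.0125 level (Sample size considerations); 1:1 allocation (Study Protocol); the boundaries (Interim analyses). Assumptions: two-sided tests; look-4 futility taken as 0.0440 rather than the printed 0.0040, so that the boundaries meet; 95% intervals unless stated.

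**Step 1: reproduce the plan's figures.** With control proportions c and experimental proportions e over the 11 categories, P(90°C better) = Σ e_j (c_1 + … + c_(j−1) + c_j/2) = 0.648. The tie-corrected Noether formula is

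N = (z_0.00625 + z_0.10)² × (1 − Σ p̄³) / [3 (P − 0.5)²], where p̄ is the mean of c and e,

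= (2.498 + 1.282)² × (1 − 0.0207) / (3 × 0.1477²) ≈ 214.

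Using the tie-corrected null variance gives 216, as printed. On the canonical four-look model, the drift for 90% power with the printed boundaries is 3.393. Inflation is (3.393 / 3.242)² = 1.096, with 3.242 = 1.960 + 1.282, and 216 × 1.096 = 237. Cumulative stopping is 8.2%, 37.2%, 75.1% and 100%, matching the plan.

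**Step 2: split the 75%.** Efficacy stops before the final look are 69.6% of trials, or 69.6 / 90 = 77% of successful ones. The other 75 − 69.6 = 5.4 points are futility stops.

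**Step 3: canonical model at the planned effect (2,000,000 trials).** The unadjusted estimate averages 1.10 times the truth over all trials and 1.30 times over early efficacy stops. For efficacy at looks 1, 2, 3 and 4 it is 2.12, 1.41, 1.05 and 0.80 times. Coverage is 92.4% for a 95% interval and 98.5% for a 98.75% interval. With no effect, the 95% interval covers 95.0%.

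**Step 4: patient-level simulation from the printed table.** Looks at 60, 118, 178 and 236 patients, printed boundaries, 6,000 to 40,000 trials. An analytic standard error stands in for the bootstrap for the probability; a 200-replicate bootstrap is used for the medians. True difference in medians: 16 points.

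| Trials | Share | Mean P(90°C better), true 0.648 | Mean difference in medians | 95% coverage for P |
|---|---|---|---|---|
| Efficacy, look 1 | 11% | 0.76 | about 46 | 66–67% |
| Efficacy, look 2 | 39–40% | 0.68 | about 25 | about 97% |
| Efficacy, look 3 | 34% | 0.637 | 12–13 | about 100% |
| All early efficacy stops | 0.964 × 0.876 = 84% | 0.675 | 22.6 | 93.9% |
| All trials | 100% | 0.662 | 19.4 | 92.3% |
| Fixed N=236, for comparison | 100% | 0.649 | 16.2 | 95.3% |

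Coverage for the difference in medians is 90.9%, against 94.5% at fixed size. For the probability, 98.75% intervals cover about 97.5%. Of the 7.7 points of misses for the probability, successful trials (96.4%, covering 94.7%) give 0.964 × 5.3 = 5.1; the other 2.6 come from trials that end without efficacy.

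Stopping here is earlier than the plan's 8%, 37% and 75% (11%, 51% and 86.5%) because the printed boundaries spend 0.05 in total, while N was set at 0.0125. With boundaries rescaled to 0.0125 and no futility stop, early efficacy stops are 0.922 × 0.758 = 70%. Coverage is then 91.6% for the probability and 91.2% for the medians, and look-3 stops are nearly unbiased (0.653).

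**Step 5: smaller effects.** At half the planned effect the canonical all-trial average is 0.97 times the truth, with 94.3% coverage. At a true 0.595 the patient-level all-trial mean is about 0.600. The rarer early stops are still too large there: 0.76 at look 1 (0% coverage, about 2.5% of trials) and 0.67 at look 2 (85%).

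**Step 6: the remedy.** At the planned effect, with futility treated as a lower bound, the stagewise interval covers 94.7% against 91.1% unadjusted. Its median-unbiased estimate exceeds the truth in 50% of trials, against 55%. After early efficacy stops it is still 1.26 times the truth, against 1.30. Repeated intervals at the printed look levels covered 95% to 99%.

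**The case against.** The strongest reply is that the harm is narrow. A reader might infer that the benefit of 90°C is overstated whenever the trial stops early. The plan's own figures do not support that. At the planned effect about a third of trials stop for efficacy at look 3, where the mean estimate is slightly below the truth and coverage is essentially complete. Final-look successes are also too low, and at clearly smaller effects the average over all trials is close to the truth. The most striking figures, 0.76 and 66%, concern 11% of trials. All of this stands.

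A reader might also take the stated 75% as the chance of stopping on a large difference. It counts futility as well; the efficacy part is about 70%.

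The 95% level is an assumption. Testing at 0.0125 makes 98.75% equally plausible, and the loss near the planned effect is then roughly 0.3 to 1 point. This limits the size of the problem, but the missing level is itself a gap.

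Finally, the remedy hardly changes the average overestimate after early efficacy stops. That is right, and it must not be presented as a cure for that bias. What it restores is overall coverage and agreement with the test. None of these replies supplies the missing adjustment.

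**Conclusion.** The concern holds in a limited form. The plan adjusts the test for four looks but not the estimates or intervals. Near the planned effect, 95% intervals lose roughly 2.5 to 4 points of coverage; at no effect they lose none. Estimates are clearly too large after efficacy stops at looks 1 and 2 and modestly too large over all early efficacy stops (0.675 against 0.648). At the planned effect they are not too large after look 3 in the patient-level run, though the canonical model gives 1.05 times the truth there. A general statement that the benefit is overstated is not supported.

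The figures assume that one time point drives stopping, that data are complete at each look and that stopping is automatic. The plan does not say which of the four time points governs. Looks are set by enrolment, so patients not yet followed up could add data after a stop and dilute the bias. The Data and Safety Committee has the final say on stopping. Effects at the other time points depend on their correlation with the one that triggers the stop.

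The stopping test is not invalidated. The reporting rule should be settled before the looks.

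**What to change.** Add a short paragraph to Data Analysis that:

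- states the confidence level of the intervals;
- states that, if the trial stops at a boundary, the primary interval for P(90°C better), the quantity the Wilcoxon test addresses, will be either a repeated confidence interval at 1 minus that look's efficacy P boundary, or a stagewise-ordering interval with its median-unbiased estimate, and names which;
- shows the unadjusted estimates and the difference in medians beside it, labelled as unadjusted for early stopping;
- says that an estimate after a very early stop may still be too large.

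With the printed boundaries, the repeated-interval levels are 99.84%, 99.52%, 98.53% and 95.60% at looks 1 to 4; if the boundaries change, the levels follow. A repeated interval stays valid if the committee departs from the boundary, but gives no corrected point estimate. Neither option applies directly to a difference in medians when a rank test drives stopping, hence the label.

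The cost is one SAP paragraph and no patients. The downside is wider intervals after an early stop.

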- 2. This prospective study will assess the relative effects of two temperatures (in degrees Celsius) used to ablate the targeted nerves in regards to pain management and possible complications.

Research Question:

Which temperature used to produce RF lesion (80°C or 90°C) is associated with better overall improvement in facet-mediated chronic low back pain?

Specific Hypotheses:

Primary

Lumbar facets medial branches RFA at 90°C provides more overall pain relief (i.e. percent of improvement), when compared to ablation at 80°C with no additional adverse events.

Secondary

Ablation of the lumbar facets nerve supply at 90°C will provide better improvement in the functionality level, general mood and quality of life as measured by VAS (Visual Analog Scale) pain score, Pain Disability Index (PDI), McGill Pain and Beck Inventory (BI) questionnaire scores than those receiving the ablation at 80°C. Furthermore, it is associated with less opioid consumption, no additional unwanted adverse events and/or complications along with less need to repeat RFA procedure over one year follow-up period.

Significance/Importance:

Chronic lower back pain (LBP) is a significant health care issue in the United States and the world. Chronic LBP contributes to decreased quality of life, decreased functionality and increased utilization of health care resources. The causes of chronic LBP tend to be multi-factorial. Arthropathy of the lumbar facet joints is thought to be a common etiology (15-45%) (1). Radiofrequency Ablation (RFA) of the medial branch nerve of the facet joint is a well-established treatment modality used to decrease facet joint pains. However, a wide range

Protocol Version 3 Revision Date: 10/15/2019 of temperature is being used (70-90 degrees Celsius). In addition, the optimal temperature that provides the best patient outcomes with the least side effects is not well established in the pain management literature.

Summary of Literature:

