correlation structure. A model-based Wald test for regression model coefficients will be used to evaluate whether or not RFA temperature affects mean pain reduction.

Opioid Consumption:

As preliminary retrospective study showed, postoperative opioid consumption is largely binary in nature for this patient's population, as over 60% of our patients did not take any opioids. Thus, postoperative opioid consumption within a year of the first RFA will be analyzed as a binary outcome, i.e., any versus none (however, dosage information among the subset of patients taking any opioids will be described using medians and quartiles for each group). Multivariable logistic regression will be used to estimate the adjusted relative risk for postoperative opioid use comparing patients undergoing RFA at 90°C to patients undergoing RFA at 80°C. A logistic model-based Wald test for regression coefficients will be used to test the hypothesis of the effect of temperature on the postoperative opioids use (i.e., whether or not the relative risk is different from a value of 1.0).

Number of repeat of RFA procedures

Need for repeated RFA procedure over one year period will be analyzed as a count variable using a proportional odds logistic regression model. If the number of repeats greater than 1 is very rare, we will use a binary outcome of any RFA procedure comparing two groups of patients.

Complications:

Incidence of each individual complication will be reported for each group, with confidence intervals. Possible adverse events (persistent paresthesia, nerve injury, bleeding and infection) will be summarized into a single composite binary outcome, i.e., any versus none. The risk of experiencing one or more adverse events will be compared between RFA at 90°C and RFA at 80°C groups using logistic regression.

Type I error will be controlled at 5% for the secondary outcomes using the Bonferroni correction for simultaneous hypotheses. SAS 9.3 software (SAS Institute, Cary, NC) and R statistical software version 2.7.2 (The R Foundation for Statistical Computing, Vienna, Austria) will be used for all analyses and graphics.

Sample size considerations:

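### Intervals for median pain relief built from a bootstrapped standard error fit poorly near the cluster of zero-relief patients, and the complication intervals have no safe method

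*Combined protocol and SAP*

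**What the plan says.** Under Data Analysis, Primary Hypothesis, the plan tests percent pain relief at 1, 3, 6 and 12 months with the Wilcoxon rank-sum test. In addition to the P-value, "the estimated median percentage of pain relief for each group and difference in medians with confidence intervals will be reported". It also asks for a probability of superiority: "The estimated probability of pain relief at 90°C being better than at 80°C with confidence interval will be reported". The paragraph closes with the method: "All the confidence intervals will be estimated based on bootstrapped standard error with 10,000 bootstrap replications". It states no confidence level.

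The Complications section, later in the same document, says: "Incidence of each individual complication will be reported for each group, with confidence intervals". It names neither a method nor a level. The primary hypothesis itself has a safety clause, expecting better relief at 90°C "when compared to ablation at 80°C with no additional adverse events".

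Sample size considerations gives the only distribution of the primary outcome. In the 80°C row, 38% of patients are at exactly zero relief and the rest are spread over ten categories up to 91-100. In the 90°C row nobody is at zero. The maximum sample size is 216 without interim analyses and 237 with them, allocated 1:1.

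**The concern.** A bootstrapped standard error is normally turned into an interval as estimate ± z × SE. That form assumes a roughly symmetric, smooth sampling distribution. A sample median close to a large block of identical zeros has neither property: its bootstrap distribution piles up at zero on one side and spreads out on the other. The symmetric interval can then miss the true median too often and can reach below 0% relief, which is outside the scale used in the planning table. The medians and their difference are the effect sizes that readers will take from the primary analysis.

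Complication incidences raise a separate problem. Every resample of an arm without events again has no events, so the bootstrapped SE is zero and the interval has no width. Such an interval would hide how large a rate the data still allow, in a trial whose primary hypothesis includes a safety clause.

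**Working it through.** **Inputs.** From Sample size considerations: the two category rows, the 15-point shift, 90% power at 0.0125, N=216 and N=237. From the Study Protocol section: 1:1 allocation, so 237/2 = 118.5 per arm. Assumed, because the plan does not say: a nominal 95% level, and the form estimate ± 1.96 × SE.

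**1. The plan's own figure.** Both rows sum to 1.000. From the table, the chance that a 90°C patient does better than an 80°C patient, counting ties as half, is 0.6477. Noether's formula gives N = (2.498 + 1.282)² / [3 × (0.6477 − 0.5)²] ≈ 218. Simulating the tie-corrected Wilcoxon test with 108 per arm gives 90.4% power. N=216 is reproduced, so the table is a sound basis for the rest.

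**2. Where the medians lie.** The 80°C row cumulates to 0.456 through 11-20 and 0.516 through 21-30, so the median is 20 + 10 × (0.500 − 0.456)/0.060 = 27.3. The 90°C row cumulates to 0.470 through 31-40 and 0.553 through 41-50, so the median is 40 + 10 × (0.500 − 0.470)/0.083 = 43.6.

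**3. Distance from the zeros.** With 119 per arm the observed zero share has SE √(0.38 × 0.62/119) = 0.0445, so the 50% point is (0.50 − 0.38)/0.0445 = 2.7 SE above the expected zero share. At a 45% zero share it is only 0.05/√(0.45 × 0.55/119) = 1.1 SE above.

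**4. Coverage.** Simulated trials with 119 per arm (an odd number, so that the median is a single observation), 6,000 per setting, values uniform within categories, and the exact bootstrap distribution of the median in place of 10,000 replications. The zero share of the 80°C arm was varied with its other categories rescaled; the 90°C arm followed the table.

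| Zero share, 80°C | True 80°C median | SE-based: 80°C median | Its lower limit below 0% | SE-based: difference | Percentile: 80°C median |
|---|---|---|---|---|---|
| 38% (plan) | 27 | 92.8% | 15% | 94.5% | 95.5% |
| 42% | 22 | 88.5% | 42% | 92.7% | 96.2% |
| 45% | 14 | 84.7% | 65% | 92.0% | 95.7% |
| 47% | 9 | 86.6% | 78% | 92.3% | 95.6% |
| 49% | 3 | 90.4% | 88% | 92.7% | 95.8% |
| 51% | 0 | 95.2% | 95% | 93.8% | 98.9% |
| 55% | 0 | 99.3% | 99% | 95.1% | 99.9% |

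Monte Carlo error is about 0.3 to 0.5 points. If answers are rounded to fives or tens, the 38% row becomes 92-94% for the single median and 93-94% for the difference, and the lowest single-median value is 84%. Percentile intervals for the difference also cover about 95-98% at zero shares of 38-48%. At a nominal 98.75% level, to match the 0.0125 criterion, the SE-based intervals cover 97-98% at 38% zeros. At 42-49% zeros they cover 91-96% for the single median and 97-98% for the difference.

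**5. Complications with no events.** The bootstrapped SE is 0, so the interval is 0% to 0% at any n. The exact (Clopper-Pearson) 95% upper limit is 1 − 0.025^(1/n): 3.1% at n = 118, and 6.1% at n = 59, about the arm size at half of maximum enrolment. The documents give no complication rates, so the following rates are assumed, with n = 118:

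| Assumed true rate | Chance of no events in one arm, (1 − rate)^118 | Coverage of the SE-based 95% interval |
|---|---|---|
| 0.5% | 0.554 | 45% |
| 1% | 0.305 | 69% |
| 2% | 0.092 | 91% |
| 3% | 0.027 | 87% |

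Four complications in two arms make eight intervals. If each true rate were 1% and the cells were independent, at least one empty cell would occur with probability 1 − (1 − 0.305)^8 ≈ 95%; at 2% it is 1 − (1 − 0.092)^8 ≈ 54%.

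**The case against.** The strongest reply concerns scope. The bootstrap sentence ends the Primary Hypothesis paragraph, directly after the requests for intervals on the medians, their difference and the probability of superiority. Its *all* most naturally refers back to those. The secondary analyses then name their own model-based Wald tests, which sit awkwardly with a document-wide bootstrap rule. This stands: a reader might infer that the plan prescribes 0% to 0% intervals for complications, but the text does not say so. On the narrow reading the plan simply names no method for them, and that is a gap in wording. Nor are these intervals the only safety evidence, because the plan also compares a composite of the four adverse events by logistic regression and sends safety assessments to the Data and Safety Committee. Neither gives an upper limit for an individual complication.

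On the medians, the reply is that the loss is small at the only zero share in the documents for the 80°C planning distribution. This also stands: one to three points for the single median and about half a point to two for the difference. A zero share of 42-48% appears nowhere in the plan. It is raised only because relief is analysed at four visits up to 12 months and the share at a given visit is unknown in advance.

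A reader might also infer that all primary-outcome intervals under-cover. The documents and the checks do not support that: no fault was shown for the probability-of-superiority interval, which is the estimate tied to the Wilcoxon null.

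**Conclusion.** The point holds for the medians as a modest but avoidable weakness, and for complications only conditionally.

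For the medians, the method is stated without ambiguity apart from the confidence level. At the plan's own distribution and 119 per arm, nominal 95% intervals cover about 93% for the 80°C median, with a lower limit below 0% in about 15% of trials, and about 94% for the difference. At an assumed 42-48% zeros this becomes about 84-88% and 90-93%. Once zeros exceed half, coverage of the single median is nominal or conservative and that of the difference is close to nominal, although lower limits below 0% remain common. These figures rest on the ± z × SE reading, the table's shape above zero, and full follow-up.

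For complications, the secure statement is that the interval method is either unspecified or, if the bootstrap sentence is applied, degenerate whenever an arm has no events. In that case 0 of 118 would be shown as 0% to 0%, although rates up to 3.1% remain open.

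The Wilcoxon tests, their significance criterion and the sample size are unaffected.

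**What to change.** - Limit the bootstrap sentence to the primary-outcome estimates. For each group median and the difference in medians, take percentile intervals from the same 10,000 replications instead of estimate ± z × SE.
- State the confidence level, and say whether it is 95% or matches the 0.0125 criterion.
- In the Complications section, name exact (Clopper-Pearson) or Wilson intervals for each incidence. Changing the type of bootstrap is not enough here, because a percentile bootstrap also returns 0% to 0% when there are no events.

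The cost is two or three sentences of SAP wording and slightly wider intervals. No extra resampling is needed, and no test, sample size or data collection changes.
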